 - 9 Slides should be submitted ≤ 30 days of enrollment, as instructed in Section 17. Central pathology review is required, but is retrospective and will not prohibit enrollment into the study.
 - 10 Correlative research blood collected prior to treatment Cycle 1 Day 1, Cycle 1 Day 2, Cycle 1 Day 3 and Cycle 2 Day 21 (see Section 14.0).
 - 11 Follow-up period is every 3 months for years 1 to 3, then yearly in years 4 and 5.
- R Research funded (see Section 19.0; patients must be willing to submit mandatory blood samples as outlined in Section 14.0).

5.0 Grouping Factors

5.1 Phase I vs. Phase II

6.0 Registration Procedures

NOTE: There is no randomization involved for this Phase I/II study. The form online is titled Registration/Randomization, but, for this trial, is meant for registration purposes only.

6.1 Phase I

Prior to discussing protocol entry with the patient, call the ACCRU Registration Office (██████████) for dose level and to insure that a place on the protocol is open to the patient.

6.11 Registration Procedures

6.111 To register a patient, fax (██████████) a completed eligibility checklist to the Academic and Community Cancer Research United (ACCRU) Registration Office between 8 a.m. and 4:30 p.m. central time Monday through Friday.

6.2 Phase II

6.21 Registration Procedures

6.212 To register a patient, access the ACCRU web page at ██████████ on “Training Page” and enter the registration/randomization application. The registration/randomization application is available 24 hours a day, 7 days a week. Back up and/or system support contact information is available on the Web site. If unable to access the Web site, call the Academic and Community Cancer Research United (ACCRU) Registration Office at (██████████) between the hours of 8 a.m. and 4:30 p.m. Central Time (Monday through Friday).

The instructions for the registration/randomization application are available by using the Help button. Prior to initiation of protocol study intervention, this process must be completed in its entirety and a ACCRU subject ID number must be available as noted in the instructions. It is the responsibility of the individual and institution registering the patient to confirm the process has been successfully completed prior to release of the study agent. Patient registration via the registration/randomization application can be confirmed in any of the following ways:

- Contact the ACCRU Registration Office ██████████. If the patient was fully registered, the ACCRU Registration Office staff can access the information from the centralized database and confirm the registration.
- Refer to “Instructions for Remote Registration” in section “Finding/Displaying Information about A Registered Subject.”

6.3 Phase I and II

6.31 Correlative Research

A mandatory correlative research component is part of this study, the patient will be automatically registered onto this component (see Sections 3.19c, 14.1 and/or 17.11).

As part of ongoing research for ACCRU lymphoma studies, paraffin-embedded tissue blocks/slides and blood products will be banked for future studies

6.32 Prior to accepting the registration, registration/randomization application will verify the following:

- IRB approval at the registering institution
- Patient eligibility
- Existence of a signed consent form
- Existence of a signed authorization for use and disclosure of protected health information

6.33 Documentation of IRB approval must be on file in the Registration Office before an investigator may register any patients.

In addition to submitting initial IRB approval documents, ongoing IRB approval documentation must be on file (no less than annually) at the Registration Office [REDACTED]. If the necessary documentation is not submitted in advance of attempting patient registration, the registration will not be accepted and the patient may not be enrolled in the protocol until the situation is resolved.

When the study has been permanently closed to patient enrollment, submission of annual IRB approvals to the Registration Office is no longer necessary.

6.34 At the time of registration, the following will be recorded:

- Patient has/has not given permission to store and use his/her sample(s) for future research to learn about, prevent, or treat cancer.
- Patient has/has not given permission to store and use his/her sample(s) for future research to learn, prevent, or treat other health problems (for example: diabetes, Alzheimer's disease, or heart disease).
- *Patient has/has not given permission for ACCRU to give his/her sample(s) to outside researchers.*

6.35 Treatment on this protocol must commence at an ACCRU institution under the supervision of a medical oncologist or hematologist.

6.36 Treatment cannot begin prior to registration and must begin ≤ 14 days after registration.

6.37 Pretreatment tests/procedures (see Section 4.0) must be completed within the guidelines specified on the test schedule.

6.38 All required baseline symptoms (see Section 10.3) must be documented and graded.

6.39a Blood draw kits must be ordered per instructions in section 14.21.

7.0 Protocol Treatment

7.1 Dosing of lenalidomide:

7.11 Phase I

R2-ICE Treatment Schedule: Cycle length is 21 days.

Agent	Dose ¹	Route	Day
Lenalidomide ²	As assigned by Randomization Center	PO	As assigned by Randomization Center
Aspirin ²	81 mg	PO	Days 1-14
Rituximab ³	375 mg/m ²	IV	Day 1
Ifosfamide	5000 mg/m ²	IV	Day 2
Mesna	5000 mg/m ²	IV	Day 2
Carboplatin	AUC 5	IV	Day 2
Etoposide	100 mg/m ²	IV	Days 1-3
Pegfilgrastim ⁴	6 mg	SubQ ⁴	Day 4
Dexamethasone ⁵	20 mg	IV ⁵	Day 1-2
Tumor lysis prophylaxis ⁶			

- 1 Body surface area based on actual body weight
- 2 For patients on the R2-ICE arm taking Lenalidomide, low dose Aspirin 81 mg daily will continue until the platelet counts fall below 50,000. Patients who cannot take aspirin will be placed on prophylactic warfarin or low molecular weight heparin (Lovenox 40 mg daily) until the platelet counts fall below 50,000.
- 3 Rituximab may be rounded to nearest 50 mg. Patients will get acetaminophen 1000 mg/dose 30 minutes prior to infusion and every 4 hours as needed for infusion related reactions (not to exceed 4000 mg/24 hours from all sources). In addition, diphenhydramine 50 mg/dose 30 minutes prior and then 25 mg/dose IV every 4 hours as needed for infusion related reactions with rituximab. This may be repeated once if symptoms are not relieved within 15 minutes of initial dose. Meperidine 25 mg/dose IV push prn rigors, may repeat once if first dose ineffective.
- 4 Pegfilgrastim should be given 18 hours after chemotherapy on Day 4-5. G-CSF (filgrastim) or other growth factors can be used (instead of Pegfilgrastim) based on institutional practice.
- 5 Dexamethasone 20 mg IV Day 1 and 2; 30 minutes prior to Rituximab and Carboplatin to prevent reactions.
- 6 Tumor lysis prophylaxis per institutional practice. For patients with AKI, large tumor burden and/or uric acid > 8 mg/dl, consideration should be given to giving rasburicase 6 mg IV once and repeated as needed.

Ifosfamide, carboplatin, and etoposide are commercially available chemotherapies that are approved by the U.S. Food and Drug Administration and other regulatory agencies for use in patients with multiple types of cancer and in various combinations. Use of these drugs to treat patients with DLBCL is considered a standard regimen in the United States.

Etoposide 100 mg/m² will be administered by IV infusion over approximately 1 hour on Days 1–3 of each cycle.

Carboplatin dose will be calculated using the Calvert formula (below) to achieve an area under the curve (AUC) of 5 mg/mL * min (maximum dose = 800 mg) and will be administered by IV infusion on Day 2 of each cycle, over approximately 1-2 hours:

Carboplatin dose in mg = 5 mg/mL*min x [GFR (mL/min) + 25 (mL/min)]
Glomerular filtration rate (GFR) will be estimated using the modified Cockcroft-Gault formula:

$$\text{GFR} = \frac{(140 - \text{age [yrs]}) \times \text{actual weight (kg)}}{72 \times \text{serum creatinine (mg/dL)}}$$

Note: Multiply by another factor of 0.85 if patient is female.

Ifosfamide 5 g/m² will be administered beginning Day 2 of each cycle by continuous IV infusion over 24 hours +/- 2 hours. Mesna 5 g/m² should be mixed in the same bag and administered in conjunction with ifosfamide. Patients may be hospitalized during this 24-hour infusion period.

Post-infusion mesna should be given in accordance with institutional guidelines (e.g. oral or IV for 6-12 hours following infusion).

Rituximab at 375 mg/m² will be administered via IV infusion per institutional guidelines. Subjects will receive 2 cycles of RICE or R2ICE before response assessment after cycle 2, or significant/serious drug related toxicity occurs. Per investigator discretion, patients can receive up to 2 more cycles of therapy before they proceed with a transplant.

ICE will be administered via IV infusion as follows: ifosfamide 5 g/m² continuously for 24 hours with mesna on Day 2; carboplatin area under the curve (AUC) = 5 mg/mL × min [800 mg maximum) on Day 2; etoposide 100 mg/m² on Days 1, 2, and 3 in 21-day cycles.

7.12 Phase II

R2ICE Treatment Schedule: Cycle length is 21 days.

Agent	Dose ¹	Route	Day
Lenalidomide ²	As determined by phase I	PO	As determined by phase I
Aspirin ²	81 mg	PO	Days 1-14
Rituximab ³	375 mg/m ²	IV	Day 1
Ifosfamide	5000 mg/m ²	IV	Day 2
Mesna	5000 mg/m ²	IV	Day 2
Carboplatin	AUC 5	IV	Day 2
Etoposide	100 mg/m ²	IV	Days 1-3
Pegfilgrastim ⁴	6 mg	SubQ ⁴	Day 4
Dexamethasone ⁵	20 mg	IV ⁵	Day 1-2
Tumor lysis prophylaxis ⁶			

- 1 Body surface area based on actual body weight
- 2 For patients on the R2-ICE arm taking Lenalidomide, low dose Aspirin 81 mg daily will continued till the platelet counts fall below 50,000. Patients who cannot take aspirin will be placed on prophylactic warfarin or low molecular weight heparin (Lovenox 40 mg daily) until the platelet counts fall below 50,000. Lenalidomide is provided at no charge to patients by Celgene Corporation for patients on the R2ICE arm.
- 3 Rituximab may be rounded to nearest 50 mg. Patients will get acetaminophen 1000 mg/dose 30 minutes prior to infusion and every 4 hours as needed for infusion related reactions. In addition, diphenhydramine 50 mg/dose 30 minutes prior and then 25 mg/dose IV every 4 hours as needed for infusion related reactions with rituximab. This may be repeated once if symptoms are not relieved within 15 minutes of initial dose. Meperidine 25 mg/dose IV push prn rigors, may repeat once if first dose ineffective.
- 4 Pegfilgrastim should be given 18 hours after chemotherapy on Day 4-5. G-CSF (filgrastim) or other growth factors can be used (instead of Pegfilgrastim) based on institutional practice.
- 5 Dexamethasone 20 mg IV Day 1 and 2; 30 minutes prior to Rituximab and Carboplatin to prevent reactions.
- 6 Tumor lysis prophylaxis per institutional practice. For patients with AKI, large tumor burden and/or uric acid > 8 mg/dl, consideration should be given to giving rasburicase 6 mg IV once and repeated as needed.

7.2 Length of Treatment: Patients will receive treatment per protocol for 2 cycles. At the end of 2 cycles, patients who are CMR, PMR, or NMR may receive a 3rd and 4th cycle of treatment per physician discretion.

7.3 Stem Cell Transplant (SCT): After the completion of 2 cycles of R2ICE treatment, patients who have achieved an objective status of CMR, PMR or NMR may proceed to SCT during the event monitoring phase. The SCT should be recorded on the event

monitoring form. Depending on the timing of the transplant, patients per physician discretion can continue treatment for a 3rd and 4th cycle prior to transplant.

7.4 For this protocol, the patient must return to the consenting ACCRU institution for evaluation at least every 21 days during treatment as specified in the test schedule (see Section 4.0).

7.5 Local Medical Doctor (LMD) treatment:

Patients must receive treatment with R2ICE per protocol at the participating ACCRU institution. However, patients are allowed to receive the *transplant* at a non-ACCRU institution.

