8.0 Dosage Modification Based on Adverse Events

Dose adjustments of ICE chemotherapy are to be performed per institutional standards. All patients will receive prophylactic hematopoietic growth factors (e.g., granulocyte-colony stimulating factor [G-CSF]) to shorten the period of neutropenia and transfusions of blood products should be provided during the course of treatment per institutional guidelines.

Standard practice and local prescribing information will be followed for rituximab and background chemotherapy. Omitting or discontinuing background therapy must lead to omitting or discontinuing of lenalidomide as well.

Dose Modifications at the start of next treatment cycles:

Dose modifications of Lenalidomide will be based on the dose levels as noted in Table 8.1 and on adverse events noted during preceding cycles (see Table 8.2 for guidance regarding dose reductions based on adverse events).

Dose modifications during a treatment cycle:

Please note, while patient is actively on Lenalidomide, modifications are not allowed during the particular treatment cycle and are only allowed Day 1 of any particular cycle. Decreasing by one dose level would be for the next cycle of treatment. During active treatment cycle, treatment can be held for up to 7 days if needed.

If multiple adverse events are seen, administer dose based on greatest reduction required for any single adverse event observed. Reductions apply to treatment given in the preceding cycle and are based on adverse events observed since the prior dose.

ALERT: ADR reporting may be required for some adverse events (See Section 10)

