9.0 Ancillary Treatment/Supportive Care

- 9.1 Antiemetics may be used at the discretion of the attending physician.
- 9.2 Blood products should be utilized as clinically warranted and following institutional policies and recommendations.
- 9.3 Patients should receive full supportive care while on this study. This includes blood product support, antibiotic treatment, and treatment of other newly diagnosed or concurrent medical conditions. All blood products and concomitant medications such as antidiarrheals, analgesics, and/or antiemetics received from the first day of study treatment administration until 30 days after the final dose will be recorded in the medical records.
- 9.4 Diarrhea: This could be managed conservatively with loperamide. The recommended dose of loperamide is 4 mg at first onset, followed by 2 mg every 2-4 hours until diarrhea free (maximum 16 mg/day).
In the event of grade 3 or 4 diarrhea, the following supportive measures are allowed: hydration, octreotide, and antidiarrheals.
- If diarrhea is severe (requiring intravenous rehydration) and/or associated with fever or severe neutropenia (grade 3 or 4), broad-spectrum antibiotics must be prescribed. Patients with severe diarrhea or any diarrhea associated with severe nausea or vomiting **should be hospitalized** for intravenous hydration and correction of electrolyte imbalances.
- 9.5 Carriers of hepatitis B virus (HBV) should be closely monitored for clinical and laboratory signs of active HBV infection and for signs of hepatitis during and for up to several months following Rituxan therapy. In patients who develop viral hepatitis, Rituxan and any concomitant chemotherapy should be discontinued and appropriate treatment, including antiviral therapy, initiated. There are insufficient data regarding the safety of resuming Rituxan therapy in patients who develop hepatitis subsequent to HBV reactivation.
- 9.6 All patients would receive growth factor support in the form of Pegfilgrastim or filgrastim (G-CSF) as per institutional guidelines and availability and coverage. Pegfilgrastim can be given 24 hours after chemotherapy on Day 4-5 but before 72 hours prior to finishing of chemotherapy. G-CSF (filgrastim) could be used starting the day after chemotherapy based on institutional practice.
- 9.7 Steroids in the form of Dexamethasone 20 mg IV Day 1 and 2 is to be given 30 minutes prior to Rituximab and Carboplatin to prevent reactions.

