- 15.193 Because of the potential for birth defects patients should be instructed in effective methods of birth control. Female patients should use 2 forms of birth control during treatment and for 4 weeks after discontinuing therapy. Males must be instructed to use a latex condom during any sexual contact with a woman of child bearing potential (even if they have had a vasectomy), because it is unknown if lenalidomide is present in semen.
- 15.194 Patients may experience pruritus, rash and dry skin. Because of the rare risk of Steven's Johnson Syndrome, patients should immediately report any rash to their provider.
- 15.195 Drug may cause hyperglycemia. Patients with diabetes or impaired fasting glucose may need to have their glucose levels monitored more closely.
- 15.196 Gastrointestinal side effects (diarrhea, constipation, nausea, dyspepsia, anorexia, etc) are commonly seen. Manage patient symptomatically and monitor for effectiveness.
- 15.197 Patients may experience myalgias, arthralgias, and other generalized pain. Administer analgesics as ordered and monitor for their effectiveness.
- 15.198 Upper respiratory symptoms (nasopharyngitis, cough, epistaxis, etc.) can be seen. Manage symptomatically and monitor for effectiveness.

15.199 Agent may cause fatigue, dizziness, vertigo or blurred vision. Instruct patients to use caution when driving or operating machines.

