Accelerated infusion rate (90 minutes): For patients with previously untreated follicular NHL and diffuse large B-cell NHL who are receiving a corticosteroid as part of their combination chemotherapy regimen, have a circulating lymphocyte count <5000/mm³, or have no significant cardiovascular disease. After tolerance has been established (no grade 3 or 4 infusion-related event) at the recommended infusion rate in cycle 1, a rapid infusion rate may be used beginning with cycle 2. The daily corticosteroid, acetaminophen, and diphenhydramine are administered prior to treatment, then the rituximab dose is administered over 90 minutes, with 20% of the dose administered over the first 30 minutes and the remaining 80% is given over 60 minutes. If the 90-minute infusion in cycle 2 is tolerated, the same rate may be used for the remainder of the treatment regimen (through cycles 6 or 8).

15.25 Pharmacokinetic information:

Duration: Detectable in serum 3-6 months after completion of treatment; B-cell recover begins ~6 months following completion of treatment;

median B-cell levels return to normal by 12 months following completion of treatment

Distribution: RA: 3.1 L; GPA/MPA: 4.5 L

Absorption: Immediate and results in a rapid and sustained depletion of circulating and tissue-based B cells

Half-life elimination: Proportional to dose; wide ranges reflect variable tumor burden and changes in CD20 positive B-cell populations with repeated doses:

Following first dose: Mean half-life: 3.2 days

Following fourth dose: Mean half-life: 8.6 days

CLL: Median terminal half-life: 32 days

NHL: Median terminal half-life: 22 days

RA: Mean terminal half-life: 18 days

GPA/MPA: 23 days

Excretion: Uncertain; may undergo phagocytosis and catabolism in the reticuloendothelial system

15.26 Potential Drug Interactions:

Increased Effect/Toxicity: Monoclonal antibodies may increase the risk for allergic reactions to rituximab due to the presence of HAC antibody. Antihypertensive medications may exacerbate hypotension.

Decreased Effect: Currently recommended not to administer live vaccines during rituximab treatment.

Herb/Nutraceutical Interactions: Avoid hypoglycemic herbs, including alfalfa, bilberry, bitter melon, burdock, celery, domain, fenugreek, grainier, garlic, ginger, ginseng, gymnema, marshmallow, and stinging nettle (may enhance the hypoglycemic effect of rituximab). Monitor.

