Acute renal failure (associated with tumor lysis syndrome), anaphylactoid reaction/anaphylaxis, angina, aplastic anemia, ARDS, arrhythmia, bowel obstruction, bronchiolitis obliterans, cardiac failure, cardiogenic shock, disease progression (Kaposi's sarcoma), fatal infusion-related reactions, gastrointestinal perforation, hemolytic anemia, hepatic failure, hepatitis, hepatitis B reactivation, hyperviscosity syndrome (in Waldenstrom's macroglobulinemia), hypoxia, interstitial pneumonitis, lichenoid

dermatitis, lupus-like syndrome, marrow hypoplasia, MI, neutropenia, optic neuritis, pancytopenia, paraneoplastic pemphigus, pleuritis, pneumonia, pneumonitis, polyarticular arthritis, pure red cell aplasia, renal toxicity, serum sickness, Stevens-Johnson syndrome, supraventricular arrhythmia, systemic vasculitis, toxic epidermal necrolysis, urticaria, uveitis, vasculitis with rash, ventricular fibrillation, ventricular tachycardia, vesiculobullous dermatitis, viral reactivation (includes JC virus [PML], cytomegalovirus, herpes simplex virus, parvovirus B19, varicella zoster virus, West Nile virus, and hepatitis C), wheezing

15.28 **Drug procurement:** Commercial supplies. Pharmacies or clinics shall obtain supplies from normal commercial supply chain or wholesaler.

15.29 **Nursing Guidelines:**

15.291 Do not administer as an IV push or bolus since it increases the risk of a hypersensitivity reaction.

15.292 Hypotension, bronchospasms, and angioedema have occurred in association with Rituxan infusion. Because of this it is recommended that patients be pre-medicated with acetaminophen and diphenhydramine before infusion. Stop infusion for severe reaction. Infusion may be restarted at 50% rate after resolution of symptoms. It is recommended that diphenhydramine, acetaminophen, epinephrine, bronchodilators, IV saline, and corticosteroids are available for immediate use in the event of a hypersensitivity reaction during administration.

15.293 Patients should be cautioned to withhold their anti-hypertensive medication for 12 hours prior to drug administration.

15.294 Patients with preexisting cardiac conditions including arrhythmias and angina have had recurrences of these events during Rituxan therapy and should be monitored throughout the infusion and immediate post-infusion period.

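### The phase II acetaminophen instruction (7.12, footnote 3) drops the daily limit of 4000 mg from all sources that the same instruction carries in phase I

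*Combined protocol and SAP*

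**What the plan says.** The rituximab footnote (footnote 3) is written out in full twice, once per phase.

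- **7.11, phase I.** Acetaminophen 1000 mg is given 30 minutes before the infusion and may be repeated 4-hourly for infusion reactions, with the limit "not to exceed 4000 mg/24 hours from all sources".
- **7.12, phase II.** Dose, timing and indication are the same, but there is no limit: "acetaminophen 1000 mg/dose 30 minutes prior to infusion and every 4 hours as needed for infusion related reactions. In addition, diphenhydramine" follows directly.

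Other text that bears on acetaminophen or analgesics:

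- Rituximab "will be administered via IV infusion per institutional guidelines" (7.11), and "Standard practice and local prescribing information will be followed for rituximab and background chemotherapy" (8.0).
- The rituximab drug section mentions acetaminophen twice: "The daily corticosteroid, acetaminophen, and diphenhydramine are administered prior to treatment" (15.24, accelerated infusion) and "it is recommended that patients be pre-medicated with acetaminophen and diphenhydramine before infusion" (15.292). Neither gives a dose or a maximum.
- Analgesics are expected during treatment. Section 9.3 has sites record "concomitant medications such as antidiarrheals, analgesics, and/or antiemetics received from the first day of study treatment administration" onward, and 15.197, on muscle and joint pain under lenalidomide, says "Administer analgesics as ordered and monitor for their effectiveness".

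**The concern.** The two phases share the rituximab dose, the infusion day and the premedication, and the protocol gives no reason for a different acetaminophen limit. The sponsor thought a ceiling was needed in phase I, so its absence from the phase II copy looks like a drafting omission.

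Two protections are lost. One is the ceiling on protocol doses. The other, more useful in practice, is the instruction to count acetaminophen from every source, since patients may be taking other analgesics.

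Most patients will be treated under 7.12. Section 16.12 plans 45 evaluable phase II patients, and 16.21 has 6 patients treated at the MTD in phase I. At most those 6 carry over, so at full accrual at least 45 − 6 = 39 patients are dosed under the uncapped wording, for 2 planned cycles and up to 4.

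**Working it through.** **Is the limit supplied elsewhere for phase II?**

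| Place | Mentions acetaminophen? | States a daily limit? |
|---|---|---|
| 7.11, footnote 3 (phase I) | Yes, 1000 mg, repeat 4-hourly as needed | Yes, 4000 mg/24 h, all sources |
| 7.12, footnote 3 (phase II) | Yes, same dose and interval | No |
| 7.11 text and 8.0 (local guidelines, standard practice) | No | No |
| 9.3 and 15.197 (analgesics) | Not by name | No |
| 10.336 (overdose definition) | No; covers lenalidomide with R-ICE only | No |
| 15.24 and 15.292 (rituximab) | Yes, as premedication | No |

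The 7.12 sentence is complete and punctuated, so the gap is neither a redaction nor a loss in text extraction. Pages removed from the text available for review could not be checked.

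**Protocol doses alone.** Inputs are 1000 mg per dose and a 4-hour minimum interval (7.12), and the 4000 mg/24 h limit (7.11). Time is counted from the premedication dose, so dose *n* falls at 4(*n* − 1) hours and the cumulative amount is 1000*n* mg.

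| Dose *n* | Hours after premedication | Cumulative mg | Ratio to 4000 mg |
|---|---|---|---|
| 1 | 0 | 1000 | 0.25 |
| 2 | 4 | 2000 | 0.50 |
| 3 | 8 | 3000 | 0.75 |
| 4 | 12 | 4000 | 1.00 |
| 5 | 16 | 5000 | 1.25 |
| 6 | 20 | 6000 | 1.50 |

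The literal maximum is 24/4 = 6 doses, or 6000 mg, which is 2000 mg (50%) above the phase I limit. With the limit restored, the maximum is 4 doses including premedication.

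**With acetaminophen from other sources.** The documents give no figure, so let *S* be an assumed amount of 0 to 3000 mg in the same 24 hours, counted in full. The limit is passed at the first *n* with 1000*n* + *S* > 4000.

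| Assumed *S* (mg/24 h) | First dose past the limit | Hours after premedication |
|---|---|---|
| 0 | 5th | 16 |
| above 0 to 1000 | 4th | 12 |
| above 1000 to 2000 | 3rd | 8 |
| above 2000 to 3000 | 2nd | 4 |

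Under the phase I wording, premedication plus one repeat (2000 mg) leaves 4000 − 2000 = 2000 mg for other sources, and premedication plus two repeats (3000 mg) leaves 1000 mg.

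**The case against.** The strongest reply is that the 6000 mg figure is a ceiling on paper. The footnote orders one premedication dose, and repeats are conditional on an infusion reaction. Rituximab is given once per 21-day cycle. According to 15.296, first-infusion reactions usually begin within the first two hours and settle when the infusion is slowed or stopped. At the suggested first-infusion rates in 15.24 (50 mg/h, rising by 50 mg/h every half hour to 400 mg/h), and assuming a body surface area of 1.5 to 2.2 m², the dose is 562.5 to 825 mg:

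- After 3 h, 525 mg has run in. The remaining 37.5 mg at 350 mg/h takes about 0.1 h, so the total is about 3.1 h.
- After 3.5 h, 700 mg has run in. The remaining 125 mg at 400 mg/h takes about 0.3 h, so the total is about 3.8 h.

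An uninterrupted infusion is therefore over before the first 4-hour repeat is due, and a fifth dose at 16 hours is improbable. In addition, the other-source range is assumed, 9.3 requires analgesics to be recorded, sites follow institutional practice, and acetaminophen is not a study drug. On this view the point is editorial: a parenthesis is missing, and nothing 7.12 says is false.

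Most of this stands as to size. The risk from protocol doses alone is low, and local practice may well apply a limit. It does not remove the inconsistency. The as-needed condition restricts when doses are given but sets no maximum. Recording an analgesic is not capping it. Local practice was equally available in phase I, where the sponsor still wrote the limit down. 7.12 also restates the footnote in full without referring back to 7.11, so a reader of the phase II table has no cue that a limit exists.

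**Conclusion.** The concern holds. The phase II instruction matches the phase I instruction in dose, interval and indication but lacks its daily limit, and no other text reviewed supplies one. As worded it permits up to 6000 mg in 24 hours against the sponsor's own 4000 mg. That figure assumes every permitted as-needed dose is given, which is unlikely. The more plausible route past the limit is acetaminophen from elsewhere that nobody is told to count, and the size of that depends on an amount the documents do not give. This is a minor safety-consistency correction that should be made. It has no bearing on the primary endpoint, the decision rules, the sample size or the error rates.

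**What to change.** In footnote 3 of 7.12, directly after the 4-hourly as-needed instruction for acetaminophen, insert in parentheses the sponsor's own phase I wording: "not to exceed 4000 mg/24 hours from all sources". Footnote 3 then sets the same acetaminophen limit in both phases. The cost is one parenthesis in the next protocol revision, with no change to sample size, timeline or analysis.
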